**Blood smear and PCR testing for assessment of *P. falciparum* parasitemia**

Blood slide preparation and reading and PCR testing will be performed according to laboratory SOPs.

**Hematological and biochemical testing**

Hematological and biochemical testing will be performed at Quest Diagnostics, Inc. using laboratory SOPs.

**APPENDIX C NHANES I CARDIOVASCULAR RISK CRITERIA**

Volunteers will be screened for cardiac risk factors and be given a screening electrocardiogram. The information will be recorded on a source document with the following noted:

Study ID # \_\_\_\_\_

**Risk factors**

Weight \_\_\_\_\_ kg

Blood pressure \_\_\_\_\_

Height \_\_\_\_\_

Smoker Y / N

Calculated BMI (kg/m^2) \_\_\_\_\_

Diabetes Y / N

**Using Table A (males) or Table B (females), 5-year cardiovascular risk:**

- Low
- Moderate
- High

**Electrocardiogram (ECG)**

12-lead ECG taken? Y / N

If not, reason \_\_\_\_\_

Electrocardiogram interpreted by:

---

Electrocardiogram interpretation:

---

Only volunteers with NHANES I low risk criteria as well as non-significant ECG, as determined by expert consultant cardiologist, are accepted in the study.

Table A (for Males)

[figure not shown]

Figure 5: Risk prediction chart for cardiovascular disease using non-laboratory-based measures (men)

**Note:** Subjects aged between 18 and 35 years will be assessed as if they are 35 (the minimum age covered by the NHANES criteria/tables). While this process likely over-estimates (minimally) the cardiac risk of these young subjects, the only associated effect would be eliminating a healthy volunteer than including a cardiac risk.

Table B (for Females)

[figure not shown]

Figure 4: Risk prediction chart for cardiovascular disease using non-laboratory-based measures (women)

**Note:** Subjects aged between 18 and 35 years will be assessed as if they are 35 (the minimum age covered by the NHANES criteria/tables). While this process likely over-estimates (minimally) the cardiac risk of these young subjects, the only associated effect would be eliminating a healthy volunteer than including a cardiac risk.

CTRS	Clinical Trial Registry Summary
eCRF	electronic Case Report Form
ES	Exposed Set
EU/ml	ELISA unit per milliliter
GMC	Geometric mean concentration
GSK	GlaxoSmithKline
HBsAg	Hepatitis B surface Antigen
ICH	Internal Conference on Harmonization
IgG	Immunoglobulin G
ITTS	Intent-To-Treat Set
IU/ml	International units per milliliter
LL	Lower Limit of the confidence interval
MedDRA	Medical Dictionary for Regulatory Activities
mIU/ml	Milli International units per milliliter
NP	Not protected
P	Protected
PCR	Polymerase chain reaction
pIMD	potential Immune Mediated Disease
PPS	Per-Protocol Set
SAE	Serious adverse event

[figure not shown]
SAP	Statistical Analysis Plan
SAS	Statistical Analysis System
SD	Standard Deviation
TFL	Tables Figures and Listings
TOC	Table of Content
UL	Upper Limit of the confidence interval
ULN	Upper Limit of normal range
VE	Vaccine Efficacy
WBC	White blood cells

1. DOCUMENT HISTORY

Date	Description	Protocol Version
20 DEC 2018	Final	Final: 26 SEP 2018

2. STUDY DESIGN

Figure 1 Study design overview

SCR = screening; **V** = visit; **D** = day; **BS** = blood sampling

*Screening visit applicable for the groups from the MALARIA-092 study receiving the fractional booster dose

**Screening visit applicable for subjects in the infectivity control group

***Blood sample for biochemistry and hematology parameters will be collected the day of first parasitemia and blood sample for assessment of parasitemia (blood smear and PCR) will be collected daily for 14 days (from Day 27 [Visit 4] to Day 40 [Visit 17]) and then every two days for nine days (Day 42 [Visit 18], Day 44 [Visit 19], Day 46 [Visit 20], Day 48 [Visit 21] and Day 50 [Visit 22]). Exceptionally this can occur within 1 or 3 days if the subject cannot make the visit or for schedule conflicts.

The following table gives the intervals between study visits at defined visits to apply, as described in the protocol:

Table 1 Intervals between study visits for the P-Fx and NP-Fx groups

Interval	Optimal length of interval*	Allowed interval**
Screening #1 → Visit 1	1 to 90 days	-
Visit 1 → Visit 2	7 days	6-8 days
Visit 1 → Visit 3 (challenge)	21 days	21-28 days
Visit 3 → Visit 22	28 days	21-35 days
Visit 22 → Visit 23	140 days	126-154 days

*Whenever possible the investigator should arrange study visits within this interval.

**Subjects may not be eligible for inclusion in the Per-Protocol Set (PPS) for analysis of immunogenicity and efficacy if they make the study visit outside this interval.

Table 2 Intervals between study visits for the infectivity control group

Interval	Optimal length of interval*	Allowed interval**
Screening #2 → Visit 3 (challenge)	1 to 90 days	-
Visit 3 → Visit 22	28 days	21-35 days

*Whenever possible the investigator should arrange study visits within this interval.

**Subjects may not be eligible for inclusion in the PPS for analysis of immunogenicity and efficacy if they make the study visit outside this interval.

The following group names will be used for the statistical analyses:

Group order in tables	Group label in tables	Group definition for footnote
1	P-Fx	Pooled subjects from the MALARIA-092 study vaccinated with RTS,S/AS01 (different doses/formulations) and protected following the first challenge who received a Fx booster dose of RTS,S/AS01E
2	NP-Fx	Pooled subjects from the MALARIA-092 study vaccinated with RTS,S/AS01 (different doses/formulations) and not protected following the first challenge who received a Fx booster dose of RTS,S/AS01E
3	Control	Subjects who did not receive any vaccination but will undergo sporozoite challenge

Two defined pooled groups:

Group order in tables	Group label in tables	Group definition for footnote
1	P	All subjects who have not been infected by P. falciparum parasitemia (defined by a positive blood slide) during the challenge in MALARIA-102 study and were part of one of the vaccinated groups
2	NP	All subjects who have been infected by P. falciparum parasitemia (defined by a positive blood slide) during the challenge in MALARIA-102 study and were part of one of the vaccinated groups

3. OBJECTIVES/ENDPOINTS

3.1. OBJECTIVES

3.1.1. Primary objective

- To assess vaccine efficacy against the occurrence of *P. falciparum* parasitemia (defined by a positive blood slide):
 - In subjects who were protected following challenge in the MALARIA-092 study and who receive a Fx booster dose versus infectivity controls.
 - In subjects who were not protected following challenge in the MALARIA-092 study and who receive a Fx booster dose versus infectivity controls.

3.1.2. Secondary objectives

Efficacy

- To assess the time-to-onset of *P. falciparum* parasitemia (defined by a positive blood slide):
 - In subjects who were protected following challenge in the MALARIA-092 study and who receive a Fx booster dose versus the infectivity controls.
 - In subjects who were not protected following challenge in the MALARIA-092 study and who receive a Fx booster dose versus the infectivity controls.

Immunogenicity

- To evaluate anti-circumsporozoite protein (CS) repeat region antibody response at specified timepoints.
- To evaluate anti-hepatitis B antigen (HBs) IgG antibody response at specified timepoints.

Safety

- To assess the reactogenicity (solicited adverse events [AEs]) and safety (unsolicited AEs, AEs of specific interest and serious adverse events [SAEs]).

3.1.3. Tertiary objectives

Efficacy

- To assess vaccine efficacy against the occurrence of *P. falciparum* parasitemia (defined by a positive blood slide):
 - In subjects who were protected versus subjects who were not protected following challenge in the MALARIA-092 study and who receive a Fx booster dose.

- To assess the time-to-onset of *P. falciparum* parasitemia (defined by a positive blood slide):
 - In subjects who were protected versus subjects who were not protected following challenge in the MALARIA-092 study and who receive a Fx booster dose.
- To assess the occurrence of *P. falciparum* parasitemia, defined by a positive PCR.
- To assess the time-to-onset of *P. falciparum* parasitemia, defined by a positive PCR.

Immunogenicity

- To evaluate the anti-CS repeat region IgG avidity index at specified timepoints.
- To evaluate the anti-full length CS protein IgG concentrations and anti-C terminal portion of the protein (C-term) IgG concentrations at specified timepoints.
- To evaluate the anti-full length CS protein and anti-C-term IgG avidity at specified timepoints.

Note: other immuno-assays evaluating the immune response targeting the CS and HBsAg might be performed.

3.2. ENDPOINTS

3.2.1. Primary endpoint

- Occurrence of *P. falciparum* parasitemia (defined by a positive blood slide) following sporozoite challenge (in all study groups versus infectivity controls).

3.2.2. Secondary endpoints

Efficacy

- Time-to-onset of *P. falciparum* parasitemia (defined by a positive blood slide) following sporozoite challenge.

Immunogenicity

- Anti-CS repeat region antibody concentrations at screening, Day 1, prior to challenge (Day 22), 28 days post-challenge (Day 50) and at study end (Day 190).
- Anti-HBs IgG antibody concentrations at screening, Day 1, prior to challenge (Day 22), 28 days post-challenge (Day 50) and at study end (Day 190).

Safety

- Occurrence of solicited local and general AEs within 7 days after vaccination (day of vaccination and 6 subsequent days) in the booster vaccination groups.

- Occurrence of unsolicited AEs up to 21 days after vaccination (day of vaccination and 20 subsequent days), according to the Medical Dictionary for Regulatory Activities (MedDRA) classification, in the booster vaccination groups.
- Occurrence of AEs up to 29 days after challenge (day of challenge and 28 subsequent days), according to the MedDRA classification, in all study groups.
- Occurrence of AEs of specific interest (potential immune-mediated diseases [pIMDs] and meningitis) from Day 1 up to study conclusion (Day 190), according to the MedDRA classification, in all study groups.
- Occurrence of SAEs (all, fatal, related to investigational vaccine) during the whole study period (from screening up to study conclusion [Day 190]), according to the MedDRA classification, in all study groups.
- Occurrence of abnormal laboratory values at screening, Day 1, Day 8, Day 22, the day of first parasitemia and 28 days post-challenge (Day 50) for the booster vaccination groups; and at screening, Day 22, the day of first parasitemia and 28 days post-challenge (Day 50) for the infectivity control subjects.

3.2.3. Tertiary endpoints

Efficacy

- Occurrence of *P. falciparum* parasitemia (defined by a positive blood slide) following sporozoite challenge (between study groups).
- Time-to-onset of *P. falciparum* parasitemia (defined by a positive blood slide) following sporozoite challenge (between study groups).
- Occurrence of *P. falciparum* parasitemia (defined by a positive PCR) following sporozoite challenge (between study groups).
- Time-to-onset of *P. falciparum* parasitemia (defined by a positive PCR) following sporozoite challenge (between study groups).

Immunogenicity

- Anti-CS repeat region IgG avidity index at Day 1, prior to challenge (Day 22), 28 days post-challenge (Day 50) and at study end (Day 190).
- Anti-full length CS protein IgG concentrations and anti-C-term IgG concentrations at Day 1, prior to challenge (Day 22), 28 days post-challenge (Day 50) and at study end (Day 190).
- Anti-full length CS protein and anti-C-term IgG avidity at Day 1, prior to challenge (Day 22), 28 days post-challenge (Day 50) and at study end (Day 190).

4. ANALYSIS SETS

4.1. Definition

4.1.1. Enrolled Set

The Enrolled Set will include all screened subjects who provide informed consent and provide any demographic and/or other baseline screening measurements, regardless of the subject's randomization and vaccination status in the trial, and receive a subject ID (for infectivity control subjects).

4.1.2. Intent-to-treat set

The Intent-To-Treat Set (ITTS) will include all subjects from the P-Fx and NP-Fx groups who received the Fx dose of study vaccine. All challenged infectivity controls will also be included and will be presented as a separate study group.

4.1.3. Solicited Safety Set

The solicited Safety Set will include all subjects who received the dose of study vaccine and had any solicited safety data.

4.1.4. Per-protocol set for analysis of immunogenicity and efficacy

The Per-Protocol Set (PPS) for analysis of immunogenicity and efficacy will include all subjects included in the ITTS who fulfilled all eligibility criteria and received the Fx dose according to protocol procedures, did not use any medication, vaccine or blood products forbidden by the protocol, did not report any underlying medical condition influencing the efficacy response, had available data concerning immunogenicity endpoint measures, and underwent *P. falciparum* challenge. This will include subjects for whom assay results are available for antibodies against at least one study vaccine antigen after Day 1.

4.1.5. Adapted Per-Protocol Set for analysis of efficacy

The Adapted PPS (APPS) for analysis of efficacy will include all subjects included in the ITTS who fulfilled all eligibility criteria and received the Fx dose according to protocol procedures and underwent *P. falciparum* challenge.

4.2. Criteria for eliminating data from Analysis Sets

Elimination codes are used to identify subjects to be eliminated from analysis. Detail is provided below for each set.

4.2.1. Elimination from Intent-to-treat set (ITTS)

Code 1030 (Study vaccine not administered at all for P-Fx and NP-Fx groups), code 800 (fraudulent data), code 900 (invalid informed consent) and code 3000 (Subject who did not undergo challenge for control group) will be used for identifying subjects eliminated from ITTS.

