##### **6.4.1.1. Contraindications to malaria challenge**

The only absolute contraindication to mosquito challenge is pregnancy. If this occurs after immunization but before undergoing challenge, the subject must not be challenged and she will be followed for the duration of the study or pregnancy whichever is longer.

A subject with a minor illness but who does not have fever during the pre-challenge assessment may be challenged at the discretion of the investigator. If the subject is

moderately to severely ill with fever on the day of the challenge, he/she will not be challenged. Challenge can be performed within the time window defined in [Table 6](#) and [Table 7](#), at the discretion of the investigator if the subject becomes well. Subjects who will not be challenged will be followed for the duration of the study.

Any conditions which according to the judgment of the investigator would make the challenge unsafe.

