### 11.4. Determination of sample size

The target enrollment for the MALARIA-092 study was ~130 vaccinated subjects (~26/vaccine group) and up to 30 subjects (or 4-6 per day, depending on the expected number of days of challenge) in the infectivity control group. Approximately 20 subjects in each group were expected to undergo sporozoite challenge (~100 vaccinated subjects overall). Based on past experience, an approximate 20% will refuse to participate in the booster study and there will be an approximate 20% drop-out rate in vaccinees for the booster study. With an assumed vaccine efficacy (VE) of ~68% in the primary study, there will be a minimum of ~20 subjects per group in this MALARIA-102 study. In addition, up to 24 infectivity control subjects will be newly enrolled for this study.

Assuming at least 19/20 controls and 6/20 vaccinees become positive (VE of ~68%), the trial has 99% power to detect statistically significant vaccine efficacy of each of the vaccination groups over the infectivity controls (p-value < 0.05).

The power to detect a statistically significant VE of each of the vaccination groups over the infectivity controls (p-value < 0.05) is presented in the table below:

Controls (N)	Vaccines (N)	Vaccine efficacy (%)	Protected controls (N)	Protected vaccinees (N)	Power* (%)
20	20	89	1	18	100
20	20	78	1	16	100
20	20	68	1	14	99.1
20	20	58	1	12	94.6
20	20	47	1	10	81.8

\*Two independent proportions power analysis - Test statistic: Fisher exact test

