### 11.5.2. Intent-to-treat set

The Intent-To-Treat Set (ITTS) will include all subjects from the P-Fx and NP-Fx groups who received the Fx dose of study vaccine. All challenged infectivity controls will also be included and will be presented as a separate study group.

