2050	Underlying medical condition forbidden by the protocol which may influence the efficacy endpoints	All	PPS
2080	Subjects did not comply with challenge schedule (see Tables 1)	All	PPS
2090	Subjects did not comply with blood sample schedule (see Tables 1)	All	PPS
2100	Serological results not available for all visits for anti-CS	All	PPS
2120	Obvious incoherence or abnormality or error in immunogenicity (antibody) data	All	PPS
3000	Subject did not undergo challenge	All	PPS, APPS

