5.5. Analysis of safety and reactogenicity

5.5.1. Analysis of safety and reactogenicity planned in the protocol

The analysis of safety will be performed on the ITTS.

For the P-Fx and NP-Fx groups:

- The percentage of subjects with at least one local AE (solicited and unsolicited), with at least one general AE (solicited and unsolicited) and with any AE during the 7-day or 21-day follow-up period after the booster Fx dose will be tabulated with exact 95% CI. Same computations will be done for grade 3 AEs, for any AEs considered related to vaccination and for any grade 3 AEs considered related to vaccination.
- The percentage of subjects reporting each individual solicited local AE (any grade and grade 3) and each individual solicited general AE (any grade, grade 3, any related, grade 3 related, resulting in medically attended visit) during the 7-day follow-up period (Days 1-7) after the booster Fx dose will be tabulated for each group, with exact 95% CI.
- For fever (defined as temperature $\geq 37.5^{\circ}\text{C}/99.5^{\circ}\text{F}$ for oral, axillary or tympanic route), the number and percentage of subjects reporting fever by half degree ($^{\circ}\text{C}$) cumulative increments during the first seven days (Days 1-7) after the booster Fx dose will be tabulated. Similar tabulations will be performed for any fever with a causal relationship to vaccination and grade 3 ($> 39.0^{\circ}\text{C}$) causally related fever. The maximum temperature reported over the 7-day follow-up period will be tabulated.
- The percentage of subjects reporting unsolicited AEs within 21 days (Days 1-21) after the booster Fx dose will be tabulated by group and by MedDRA preferred term with exact 95% CI. Similar tabulation will be done for grade 3 unsolicited AEs, for any causally related unsolicited AEs and for grade 3 causally related unsolicited AEs.
- The percentage of subjects using concomitant medication (any medication, any antipyretic and any prophylactic medication, respectively) during the 7-day follow-up period after vaccination will be summarized by group.

For all subjects:

- The percentage of subjects reporting AEs during 29 days after the sporozoite challenge (Day 22-Day 50) will be tabulated by group and by MedDRA preferred term with exact 95% CI. Similar tabulation will be done for grade 3 unsolicited AEs, for any causally related unsolicited AEs and for grade 3 causally related unsolicited AEs post challenge.

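### Post-challenge adverse event and medication percentages use a set that keeps vaccinees who were never challenged but contains only challenged controls

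*SAP*

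**What the plan says.** SAP 5.5.1 sets one population for all safety output: "The analysis of safety will be performed on the ITTS". Protocol 11.11 agrees.

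The ITTS has a different entry rule for each type of group. On the vaccinated side it "will include all subjects from the P-Fx and NP-Fx groups who received the Fx dose of study vaccine" (SAP 4.1.2), with no requirement to have been challenged. For controls, Protocol 11.5.2 says: "All challenged infectivity controls will also be included and will be presented as a separate study group". The elimination rule in SAP 4.2.1 matches this: "code 3000 (Subject who did not undergo challenge for control group) will be used for identifying subjects eliminated from ITTS". In the table in SAP 4.2.3.1 the same code reads "Subject did not undergo challenge" and applies to the per-protocol set (PPS) and adapted PPS with no limit by group.

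Among the tables for all subjects, SAP 5.5.1 plans: "The percentage of subjects reporting AEs during 29 days after the sporozoite challenge (Day 22-Day 50) will be tabulated by group". Versions for grade 3, related, and grade 3 related events follow, and concomitant medication on Days 22-50 is summarised by group. AE occurrence after challenge in all study groups is a secondary safety endpoint (Protocol 11.2, SAP 3.2.2).

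Vaccinees who go unchallenged are foreseen. Protocol 6.4.1.1 names pregnancy, febrile illness on the day and investigator judgement, and adds: "Subjects who will not be challenged will be followed for the duration of the study".

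**The concern.** A percentage of subjects with an AE after challenge needs a denominator of challenged subjects. The control group has one by definition. The vaccinated groups have one only if nobody is lost between booster and challenge, an interval of 21 to 28 days (Protocol Table 6).

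If someone is lost, the percentages shown side by side no longer measure the same thing. The vaccinated figure becomes a mixture of challenged and unchallenged subjects, while the control figure stays pure. Because malaria symptoms follow challenge, the mixture will usually read low. P-Fx and NP-Fx would also differ from each other if their numbers of unchallenged subjects differ. What is at stake is the accuracy of a secondary safety endpoint, not a test or an efficacy result.

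**Working it through.** **Step 1. Entry rules side by side**

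| Set | P-Fx and NP-Fx | Controls |
|---|---|---|
| ITTS (SAP 4.1.2, 4.2.1) | Fx dose received; challenge not required | Challenged only |
| PPS and adapted PPS (SAP 4.2.3.1, code 3000) | Challenged only | Challenged only |

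The SAP defines a Solicited Safety Set for the solicited-event phase (4.1.3) but nothing equivalent for the challenge phase.

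**Step 2. The plan's own group size**

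Protocol 11.4 starts from about 100 vaccinees challenged in MALARIA-092 and assumes about 20% refusal, about 20% drop-out and about 68% efficacy:

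- 100 × 0.80 × 0.80 = 64 subjects
- NP-Fx: 64 × 0.32 = 20.5
- P-Fx: 64 × 0.68 = 43.5

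The stated minimum of about 20 per group is reproduced, and 20 is used below.

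**Step 3. Effect of unchallenged vaccinees**

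Let N be the number vaccinated in a group, u the number of these not challenged, r the AE proportion in the challenged and q the Day 22-50 AE proportion in the unchallenged.

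- ITTS percentage = [(N − u) r + u q] / N
- Shift from r = −(u/N)(r − q)
- If q = 0, ITTS percentage = r × (N − u)/N

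The documents give none of u, r or q, so these are assumed values shown over a range. With N = 20 and q = 0:

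| u | Factor | Example: challenged only | Same events on the ITTS |
|---|---|---|---|
| 0 | 1.00 | 10/20 = 50.0% | 10/20 = 50.0% |
| 1 | 0.95 | 17/19 = 89.5% | 17/20 = 85.0% |
| 2 | 0.90 | 9/18 = 50.0% | 9/20 = 45.0% |
| 4 | 0.80 | 8/16 = 50.0% (95% CI 24.7-75.3) | 8/20 = 40.0% (95% CI 19.1-63.9) |

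The intervals are Clopper-Pearson, the SAP's exact method. The control factor is always 1.00.

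**Step 4. Sensitivity to q**

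With N = 20, u = 2 and r = 50%:

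- q = 0: 9/20 = 45.0%
- q = 25%: (18 × 0.50 + 2 × 0.25)/20 = 9.5/20 = 47.5%
- q = 50%: (9 + 1)/20 = 50.0%, no shift

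The percentage falls only if unchallenged vaccinees have fewer Day 22-50 events than challenged ones.

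**Step 5. An extreme case**

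Protocol 11.4 expects that "there will be an approximate 20% drop-out rate in vaccinees for the booster study" but does not say at what stage. If all of it fell between booster and challenge, NP-Fx would have 100 × 0.80 × 0.32 = 25.6, about 26, vaccinated and 26 × 0.20 = 5.2, about 5, unchallenged. The factor is 21/26 = 0.81, so 19/21 = 90.5% would become 19/26 = 73.1%. This is a ceiling under an assumption the documents do not make, not an expectation.

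**The case against.** **The entry rule is principled.** Each group enters the ITTS at its first study intervention: vaccination for P-Fx and NP-Fx, challenge for controls. Protocol 5.1 equates enrolment of a control with undergoing challenge. This stands, and the ITTS definition need not change. It does not make that set the right denominator for a post-challenge table.

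**The denominator may be settled elsewhere.** Protocol 11.6 says unsolicited AE and medication analyses consider all subjects so far as applicable, and the table shells are filed outside the SAP. But the qualifier is undefined, SAP 5.5.1 does not repeat it, and shells that cannot be seen do not override a stated population. The rule in Protocol 11.6 that counts missed reports as no symptom concerns subjects who failed to report. It does not address subjects who were never challenged, so it settles nothing either way.

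**Unchallenged vaccinees can have events.** This stands. They remain in follow-up, the tables carry a calendar window, and someone too ill to be challenged may well report an AE or take medication on Days 22-50. The 5% figure therefore depends on q = 0. Such an event would, however, be tabulated as occurring after a challenge that did not take place.

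**The consequence is limited.** A reader might infer that vaccinees will appear to tolerate challenge better than controls purely through attrition, by as much as in Step 5. The documents do not support that. They give no expected number of unchallenged vaccinees and do not place the drop-out before challenge, in an interval of 21-28 days within a study of about seven months. An effective vaccine should itself reduce post-challenge AEs by preventing malaria, so a lower percentage in vaccinees would not be purely an artefact. No between-group safety test is planned, and SAP section 6 calls all analyses descriptive.

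**Conclusion.** The point holds as a mismatch between a set and the tables built on it. As written, any vaccinee who received the fractional dose but was not challenged stays in the denominator for post-challenge AEs (any, grade 3, related) and Day 22-50 medication, whereas the control group contains only challenged subjects. The vaccinated percentages then do not estimate occurrence after challenge and are likely to be lowered.

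In a group of 20 the size is 5% in relative terms per unchallenged vaccinee, assuming no Day 22-50 event in those subjects. It is smaller if they have events and zero if every vaccinee is challenged. How many will go unchallenged cannot be known from the documents. No error rate or efficacy result is affected. The correction is still worth making before analysis, because these percentages and their exact intervals are the planned group summary of post-challenge AEs.

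**What to change.** In SAP 5.5.1 and Protocol 11.11:

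- Base the post-challenge AE tables (any, grade 3, related, grade 3 related) and the Day 22-50 concomitant medication table on ITTS subjects who underwent challenge, applying code 3000 to all three groups for these tables only.
- Keep the full ITTS for vaccination-phase AEs, and for SAEs and AEs of specific interest counted from Day 1.
- List Day 22-50 events in unchallenged vaccinees separately, so that none is lost.
- Add to the study flow table (Protocol 11.7, SAP 5.1.1) the number vaccinated but not challenged, by group and reason. The table as described goes from receipt of the Fx dose to the PPS with no row for challenge.

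The cost is a few lines of wording and a denominator flag from a code the SAP already uses. No new data are needed. If the protocol is not amended, record the change in SAP section 8 and justify it in the study report, as Protocol 11.13 requires.
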